## **6 ADDITIONAL STATISTICAL CONSIDERATIONS**

### **6.1 Descriptive Statistics and General Analyses Methods**

All data collected will be listed. Continuous data will be described by the number of non-missing observations, mean, median, minimum value, maximum value and the standard deviation. Categorical data will be summarised by the number and proportion in each category. Confidence intervals will be two-sided and at the 95% confidence level. Figures as appropriate to further describe the data may be presented.

See Section 8 for further information of statistical analysis.

### **6.2 Missing, Unused or Spurious Data**

Missing data will not be imputed.

### **6.3 Visit Windows**

This is a single visit study with no visit windows applicable.

### **6.4 Imputation of Partial Dates**

This is a study conducted at a single visit. There are no outcomes that are time dependent to be reported.

### **6.5 Covariates**

Not applicable

### **6.6 Subgroup Analyses**

No subgroup analyses are planned.

## **6.7 Additional Statistical Analyses**

Not applicable

## **7 SUBJECT INFORMATION**

### **Demographic and baseline Characteristics**

Demographic and baseline characteristics collected in this study will be summarised appropriately for the safety population. Baseline characteristics will include summaries of hearing history, device history (hearing aid and implant), medical history and medications commenced prior to screening.

### **Subject Disposition**

Subject disposition will be summarised with reasons for discontinuation for the safety population. Additionally, the reason for exclusion from the per-protocol population will also be presented with details of the deviations.

### **Extent of Exposure and Duration of Follow-Up**

The study is a single visit study, with up to 3 hours of testing per subject. Any deviations from this plan will be listed in the clinical investigation report.

### **Protocol Deviations**

Major protocol deviations will be listed for the safety population with the reason(s) for the deviation(s).

### **Concomitant Medications**

Concomitant medications received during the study will be summarised appropriately for the safety population.

## **8 STATISTICAL ANALYSES**

### **8.1 Efficacy Analysis**

#### ***Primary and Secondary Speech Perception Endpoints:***

Words in quiet scores at different speech testing conditions will be listed and summarised descriptively by treatment group and study population. Figures as appropriate to further describe the data may be presented.

For the non-inferiority test of words in quiet scores, the 95% CI (alpha=0.025 one-sided) for the mean paired difference will be estimated. If the lower limit of the 95% CI of the mean paired difference is above -10%, the treatment condition is regarded as non-inferior to the control in term of words in quiet perception. The non-inferiority margin of -10% for words in quiet scores (monosyllables) is also based on clinical consensus.

While sequence and period effects are expected to be minimal in this single day, in booth study of approximately 3 hours duration, an analysis of variance (ANOVA) that considers the sequence and period effects will also be conducted as a supportive analysis to the paired t-test. The model will be formulated as follows:

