7.2 Subjects

The subjects include men and women aged 18 years or older who are current users of a Nucleus 6 (CP910/920), Kanso 2 (CP1150), Kanso (CP950) or Nucleus 7 (CP1000) Sound Processor. Subjects will be screened, and 20 eligible subjects will be recruited to the clinical investigation. For speech perception testing, all subjects will receive all treatment and control conditions; however, the test order will be counterbalanced to control for order effects.

Written, informed consent must be obtained from the subject before any study procedures are initiated.

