7.2.3 Number of Subjects Required

The total number of subjects to be enrolled in the study to meet sample size calculation requirements is 12, which includes 3 additional subjects to account for an expected dropout rate of 25%.

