7.2.6 Criteria for Subject Withdrawal

Subjects can decide to withdraw from the investigation at any time. The Investigator shall ask the reason(s). The reason for withdrawal should be documented in the subject's source files and the case report form (CRF).

The Investigator or Sponsor may also decide to withdraw a subject from the clinical investigation if it is considered to be in the subject's best interests.

Subject withdrawal may be for any of the following reasons:

- Adverse Event (AE)
- Device Deficiency (DD)
- CIP or GCP deviation
- Subject withdrew consent
- Subject lost to follow-up
- Subject death
- Sponsor decision
- Investigator decision
- Other (specify)

If a subject is lost to follow-up, every possible effort must be made by the study site personnel to contact the subject and determine the reason for discontinuation. At least 3 separate attempts taken to contact the subject must be documented.

Participating subjects who are withdrawn/discontinued will not be replaced.

Clinical Investigation Plan: CLTD5818

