7.2.7 Randomisation Procedures

No treatment randomisation is planned. However, to control for order effects during speech perception testing for the Primary and Secondary Endpoints a 4x4 balanced Latin square order will be implemented (see table 3).

	First Sound Processor	Second Sound Processor	Third Sound Processor	Fourth Sound Processor
SYD01, 05, 09	Kanso 2	Kanso 2 NF	Nucleus 8	Kanso 2 + FF
SYD02, 06, 10	Kanso 2 NF	Kanso 2 + FF	Kanso 2	Nucleus 8
SYD03, 07, 11	Kanso 2 + FF	Nucleus 8	Kanso 2 NF	Kanso 2
SYD04, 08, 12	Nucleus 8	Kanso 2	Kanso 2 + FF	Kanso 2 NF

Table 3. Order of Administration of the Speech Perception Tests

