9.4 Sample Size Determination

This study is a non-inferiority design, and sample size calculation was based on non-inferiority tests for CNC word scores. The sample size using a confidence interval method (two-tailed 95% confidence interval) was estimated to have a reasonable power to detect non-inferiority word scores for the listed hypotheses.

To reject the null hypothesis of inferior word perception in quiet for the New processor:

- A margin of non-inferiority of 10% (new-old) has been chosen. That is saying that a true mean difference of anything up to 10% is acceptable and not clinically meaningful. This margin is based on clinical consensus, and previous feedback from the FDA
- An expected standard deviation of difference scores of 7.5% for CNC words (50 dB), based on previous OTE studies investigating words in quiet.
- A significance level $\alpha = 0.05$ (two-tailed).
- A desired power of 0.9.

Based on these assumptions, a sample size of 9 subjects is required to reject the null hypothesis. An increased sample size of 12 subjects will be enrolled, which will allow for the possibility that the variability in difference scores will be greater than expected and to account for the possibility of subject attrition.

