9.5 Analysis Populations

The analysis of the primary endpoint will be based on the Intent-To-Treat (ITT) and Per Protocol (PP) analysis populations in order to support a conclusion of non-inferiority. The inclusion of both ITT and PP populations has been chosen to assess the robustness of the study results and the consistency of the study measures under different analysis populations.

This study has a non-inferiority design; therefore, the primary analysis will be based on the PP population.

For cases in which the ITT and PP populations lead to the same conclusions and final interpretations about the treatment effect, the results will be considered to not be influenced by underlying factors such as missing data and protocol deviations, and the results would be considered to be robust and consistent under different analysis populations. A statement to reflect this will be included in the CIR.

For cases in which the ITT and PP populations lead to different final interpretations or conclusions, all of the results will be reported and the differences in outcomes will be identified and explored.

Intent-to-Treat Population

The Intent-to-Treat Population will include all subjects who receive the treatments and have at least one set of paired treatment and control measurements from any endpoint, regardless of protocol deviations and missing data.

Per Protocol Population

The Per Protocol Population will include all subjects who receive the treatments and have at least one paired measurement from treatment and control, without major protocol deviations. Major deviations will be defined at the clean file meeting before data base lock.

It is possible that a treatment has not been administered in the intended counterbalanced order of presentation.

It is also expected that the sequence and period effects are minimal in this study if any. This study is not a full cross-over design, so period and sequence effects will not be assessed, without the consequence to bias the study conclusion.

Safety Population

The Safety Population will include all treated subjects. The Safety Population will be used for the safety data analysis.

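### Should the non-inferiority decision rest on the period-adjusted ANOVA instead of the paired t-test, given that the protocol and SAP disagree on assessing order effects?

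*SAP*

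**What the plan says.** **Design.** Protocol 7.2 states that "all subjects will receive all treatment and control conditions". Under Protocol 7.2.7, "a 4x4 balanced Latin square order will be implemented", and Table 3 assigns three subject numbers to each of four orders. SAP 1.4 repeats this.

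**Protocol on order effects.** Section 9.5 says: "This study is not a full cross-over design, so period and sequence effects will not be assessed". It adds that this is "without the consequence to bias the study conclusion".

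**SAP on order effects.** SAP 5.2 omits that statement and expects the effects to be negligible. SAP 8.1 adds an ANOVA with device, period, sequence and subject within sequence. It reports the least squares mean difference with a 95% CI, and this "will also be conducted as a supportive analysis to the paired t-test".

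**Decision rule.** In both documents, non-inferiority is declared if the lower 95% limit of the mean paired difference lies above -10 points, with the per-protocol set primary. The only rule for conflicting results concerns ITT against per-protocol (Protocol 9.5, SAP 5).

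**Attrition.** Twelve subjects are enrolled so that 9 remain after 25% dropout (Protocol 7.2.3). Protocol 7.2.6 says: "Participating subjects who are withdrawn/discontinued will not be replaced". SAP 5.6 counts a wrong test order as a major deviation, which takes the subject out of the per-protocol set.

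**The concern.** Three things look wrong at first reading.

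- The protocol misdescribes its own design and draws from that a reason to leave order unexamined. The SAP then examines it.
- The decisive test ignores period. The protocol's assurance of no bias is secure when the four orders are equally represented, and the plan itself foresees losing up to three of the twelve subjects. If scores drift over the session through practice or fatigue, an unbalanced per-protocol set shifts the paired mean. Even a balanced set gives a wider interval than the design needs.
- The SAP will produce two 95% intervals for the same contrast, and neither document says what to conclude if only one clears -10.

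At stake would be the planned power at 9 completers, the error rate in badly unbalanced sets, and room for an after-the-fact reading in an open-label study run by sponsor employees.

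**Working it through.** **Inputs.** From Protocol 9.4 and SAP 1.3: margin 10, SD of paired differences 7.5, two-sided alpha 0.05 (one-sided 0.025), power 0.9, n = 9. Assumed: true difference 0 for power, and a linear drift of b points per period common to all subjects. The documents give no b; 0, 1 and 2 are shown.

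**1. The plan's own figure.** For the paired t-test, the noncentral t with noncentrality 10/(7.5/√n) gives power 0.896 at n = 8 and 0.937 at n = 9. So 9 is reproduced, and 9/(1 - 0.25) = 12. At n = 12 the power is 0.987.

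**2. The design.** In Table 3 each device occurs once in each period, and each of the 12 ordered neighbour pairs occurs once. This is a complete four-period crossover. Position differences in sequences 1 to 4 are:

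| Comparison | Seq 1 | Seq 2 | Seq 3 | Seq 4 | Sum | Mean square |
|---|---|---|---|---|---|---|
| NF - Kanso 2 | +1 | -2 | -1 | +2 | 0 | 2.5 |
| FF - Kanso 2 | +3 | -1 | -3 | +1 | 0 | 5 |
| Kanso 2 - Nucleus 8 | -2 | -1 | +2 | +1 | 0 | 2.5 |

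**3. Bias.** Shift = b × Σ(n_s × d_s)/Σn_s, where d_s is the position difference and n_s the completers in sequence s. With three per sequence every sum is 0, so there is no shift. The worst upward shifts at 9 completers come from losing a whole sequence:

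- NF without sequence 2: (3 - 3 + 6)/9 = 0.67b.
- FF without sequence 3: (9 - 3 + 3)/9 = 1.0b.

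Each of these is 1 of the 220 ways to keep 9 of 12.

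**4. Precision with 12 completers.** SD = √(7.5² + (12/11) × mean square × b²). At b = 2 this is √(56.25 + 10.91) = 8.2 for NF and √(56.25 + 21.82) = 8.8 for FF. Twelve completers hold 90% power up to an SD of 9.71. That corresponds to b of about √((94.3 - 56.25)/2.727) = 3.7 for NF and √((94.3 - 56.25)/5.455) = 2.6 for FF.

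**5. Simulation of both analyses.** Error SD per score is 7.5/√2. The ANOVA has 30 residual df with 12 completers and 21 with 9; the paired t-test has 11 and 8. Figures for 9 completers are averages over all 220 subsets.

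| Setting | Paired t | ANOVA |
|---|---|---|
| 12 completers, b = 0, mean half-width | 4.7 | 4.4 |
| 12 completers, b = 2, mean half-width NF / FF | 5.1 / 5.5 | 4.4 |
| 12 completers, b = 2, power NF / FF | 0.98 / 0.97 | 0.99 |
| 9 completers, b = 0, power | 0.94 | 0.96 |
| 9 completers, b = 1, power NF / FF | 0.93 / 0.92 | 0.96 |
| 9 completers, b = 2, power NF / FF | 0.90 / 0.87 | 0.96 |
| 9 completers, b = 2, average one-sided error NF / FF | 1.9% / 1.5% | about 2.5% |
| Sequence 2 lost (NF) or 3 lost (FF), b = 2, one-sided error | 5.7% / 7.6% | about 2.5% |

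**6. What the ANOVA costs.** It pools residual variance over all four devices. With 12 completers, no trend and Nucleus 8 scores having a 50% larger SD, its one-sided error for Kanso 2 against Nucleus 8 is about 3.8%, against 2.5% for the paired t-test. If NF and Kanso 2 scores both have a 25% larger SD, its error for NF is about 3.7%, against 2.5%.

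**7. How often the two intervals disagree on non-inferiority.** At a true difference of 0 with 12 completers: 0.9% of trials with no trend, and 1.8% (NF) and 2.8% (FF) at b = 2. With 9 completers: 4.3%, then 7.4% and 10.7%.

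**8. Requiring both intervals to clear -10.** This would hold one-sided error at or below 2.2% in every case simulated, but it gives up the ANOVA's power. For FF at 9 completers and b = 2, power is 0.860, against 0.865 for the paired t-test alone.

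**The case for a change.** The best case for a change is that both analyses are already specified, so exchanging their roles costs only wording. The ANOVA removes any common trend, keeps its error near 2.5% in unbalanced sets when variances are equal, and holds power at 0.96 where the paired t-test can fall below the target ("A desired power of 0.9") for FF. Disagreement is also less rare if the true difference is not 0: at -5 with 12 completers and no trend, the two intervals differ in about 12% of trials. A reading fixed before database lock would be cleaner than one chosen once both are visible.

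The factual parts of this stand: the protocol sentence is wrong, it conflicts with the SAP, and a real trend would cost precision. The remedies do not follow.

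- **Correcting the protocol sentence** changes no analysis, because SAP 8.1 already fits the model. Protocol section 18 would still require an agreed amendment and ethics committee notification.
- **Making the ANOVA decisive** exchanges a test that needs no equal variances across devices, and whose average error stays at or below nominal, for one that can exceed nominal in the full planned design. Its gain depends on a trend that both documents expect to be minimal.
- **A disagreement rule** would add little. The paired interval decides, the ANOVA is labelled supportive, and its interval must be reported anyway. Calling a discordant result not robust is what a competent report would do. A label of that kind does not lower the error rate; only requiring both intervals to clear -10 would, and step 8 shows that this removes the power gain.

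**Conclusion.** No change to the plan is needed. The protocol's description of the design is a clerical slip that the SAP, written later as the protocol's companion, has overtaken. The choice of decisive analysis is a fair trade-off, and the reading of a discordant supportive ANOVA is a gap that analysts will fill sensibly.

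With 12 completers in the planned orders, the paired t-test is unbiased and has power of at least 0.97 even at 2 points per period. At 9 completers and 1 point per period it still has 0.93 (NF) and 0.92 (FF). Falling below 0.9 takes the full planned attrition together with a shared drift of about 2 points per period, and then it affects FF, a secondary comparison; the primary comparison stays at about 0.90. Error well above nominal needs the loss of particular sequences as well as a trend. At 9 completers and 2 points it exceeds 3% in 13% of subsets, while the average stays at 1.5 to 1.9%.

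These figures assume an SD of 7.5, a true difference of 0 for power, and a linear trend common to all subjects. A documented drift well above 2 points per period would strengthen the case for the ANOVA; neither document suggests one.

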**QMS Document**

*For Internal Use Only*

CNC words in quiet (% correct) = device + period + sequence + subject (nested in sequence)

The least squares mean difference in CNC words (in quiet) estimated by the ANOVA model will be provided along with a 95% confidence interval.

If non-inferiority is demonstrated, the testing will proceed to a test of superiority.

These results will also be presented graphically illustrating the observed mean, its 95% CI and the non-inferiority margin as defined by the hypothesis test.

**8.2 Safety Analysis**

Incidence of adverse events (AE/ADE) will be presented. Additionally, the severity, relationship to treatment, outcome and actions taken will be listed for each subject. Likewise, the devices deficiencies (DD) will also be reported as incidences and listed.

For AE/ADEs and DDs, the percentage of subjects who experienced at least one occurrence of each, will be summarised. Any subjects who died, who discontinued an intervention due to an AE/ADEs, or who experienced a severe or an SAE/SADEs will be summarised separately.

**8.3 Other Analyses**

Not applicable

**10 CHANGE HISTORY**

Version	Change	Author	Date
1.0	Introduction of the document	██████████	refer to e-signature record

